## • Primary Efficacy Endpoint

Following the American Association for the Study of Liver Diseases-Journal of the National Cancer Institute guidelines for trial design in HCC, we have set our primary endpoint as TTR, according to the recommendation for Phase II studies that assess adjuvant therapies secondary to liver directed therapy (33). TTR will be defined as the time from randomization to the first occurrence of a documented HCC recurrence or HCC death, within the 12-month intervention and assessment period. Participants who experience death attributed to their underlying liver cirrhosis, or other cause, will be censored at death date. For participants who do not recur or die and are lost to follow-up prior to the 12-month study visit, analysis of TTR will be censored at their last date of evaluable scan before drop-out.

In this study, we will rely heavily on the mRECIST outcome guidelines and the Liver Imaging Reporting and Data System (LI-RADS) diagnostic algorithm for defining hepatic recurrence (34, 35), and central expert independent radiographic review by MedQIA.

Pathological Definition: Participants who receive a transplant will become ineligible at the time of transplantation. Recurrent HCCs may also be identified at time of transplantation during the examination of the explant by a pathologist. These "incidental" HCCs represent a sizable proportion, amounting to 22% of HCCs among those receiving a liver transplant. Thus, if transplantation occurs and a pathologically confirmed HCC is detected, we will examine these pathologically defined tumors as a **secondary** definition of recurrence.

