#### • Secondary Efficacy Endpoints

Secondary endpoints include recurrence-free survival (RFS), overall survival (OS), waitlist survival, liver stiffness, liver fat fraction, circulating biomarkers, and liver tissue biomarkers. Differences in secondary endpoints will be compared in the pravastatin and placebo groups.

1) RFS: We will assess the effect of pravastatin on RFS. RFS will be defined as the time from randomization to the first occurrence of a documented HCC recurrence, within the 12-month intervention and assessment period.

2) OS: We will examine the effect of pravastatin on OS (defined as the time from randomization to death from any cause).

3) Waitlist drop-off: We will evaluate the effect of pravastatin on reducing waitlist dropout due to any of the following causes: 1) HCC progression outside of Milan/T2 criteria, 2) cirrhosis progression (too sick to transplant), or 3) death.

Participants who are delisted for other reasons (such as positive alcohol test) will be censored at date of delisting.

4) Change in liver stiffness: We will evaluate the effect of pravastatin on withinperson change in liver stiffness, as measured by magnetic resonance elastography (MRE) or FibroScan, between Study Visit 1 (0 month) and Visit 6 (12 month). Within-patient consistency is required between Study Visits 1 and 6 with regards to liver stiffness testing modality (MRE or FibroScan).

5) Change in liver fat fraction: We will evaluate the effect of pravastatin on withinperson change in liver fat fraction, as measured by MRI-proton density fat fraction (PDFF), between Study Visit 1 (0 month) and Visit 6 (12 month).

6) Change in serum biomarkers of monocyte/macrophage and stellate cell activation: We will examine the effect of pravastatin on change in serum biomarkers including cytokines, chemokines, soluble receptors, and proteins (specifically, IL6, TNF $\alpha$ , sTNFRII, IL18BP, sCD163, IL10, IL17, IL-8, CCL17, TGF $\beta$ ).

7) Levels of liver tissue markers related to HCC: We will examine the effect of pravastatin on levels of liver tissue markers related to HCC including those in the Wnt/ $\beta$ -catenin pathway (specifically,  $\beta$ -catenin and glutamine synthetase).

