## 9.3 Study Endpoints

We have set our primary endpoint as TTR. Secondary endpoints include RFS, OS, waitlist survival, liver stiffness, and circulating biomarkers. Differences in secondary endpoints from baseline to 12-month follow-up will be compared in the pravastatin and placebo groups using a similar approach to the main endpoint.

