# 9.3.2 Analysis of Secondary Endpoints RFS and OS

For the secondary objective, comparison of overall survival and recurrence free survival between the pravastatin and placebo groups will be achieved by fitting a Cox proportional hazards model as described above for TTR. In this analysis, a competing risk model will

be fitted to the data using time to transplant only as a competing risk since overall survival includes death from any cause.

**Waitlist drop-off.** Fischer's exact test will be used to compare the proportions of patients on the waitlist who drop off between the pravastatin and placebo group. We expect about 35% of patients in the placebo group to drop off due to various causes such as death and HCC progression beyond Milan. Data from 47 patients per group achieve 80% power to detect a decrease in drop-off rates from 35% in the control group to 14% in the treatment group using a one-sided Fisher's exact test at the 0.1 level of significance.

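### Waitlist drop-off is defined with censoring at delisting but tested with Fisher's exact test, which cannot censor, and the plan gives no rule for transplanted participants

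*Combined protocol and SAP*

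**What the plan says.** Section 2.3 (Secondary Efficacy Endpoints) defines drop-off by cause: "1) HCC progression outside of Milan/T2 criteria, 2) cirrhosis progression (too sick to transplant), or 3) death". It then gives a rule for everyone else who leaves the list: "Participants who are delisted for other reasons (such as positive alcohol test) will be censored at date of delisting".

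Section 9.3 renames the endpoint: "Secondary endpoints include RFS, OS, waitlist survival, liver stiffness, and circulating biomarkers". It adds that secondary endpoints will be handled much as the primary one is. Under Section 9.3.1 that means log-rank, Cox and competing-risk methods.

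Section 9.3.2 departs from this for drop-off alone: "Fischer's exact test will be used to compare the proportions of patients on the waitlist who drop off". The power statement there reads "Data from 47 patients per group achieve 80% power to detect a decrease in drop-off rates". It specifies "a decrease in drop-off rates from 35% in the control group to 14% in the treatment group" and a "one-sided Fisher's exact test at the 0.1 level of significance".

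On transplant, Section 2.3 (Primary Efficacy Endpoint) says: "Participants who receive a transplant will become ineligible at the time of transplantation". Sections 9.3.1 and 9.3.2 treat transplant as a competing risk for time to recurrence, RFS and OS. Neither gives a rule for drop-off. Section 3.0 describes the 47 per group as those left once transplantation and cirrhosis death have been allowed for.

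**The concern.** An analyst following Section 9.3.2 cannot carry out Section 2.3. A participant delisted in month 2 for a positive alcohol test must be counted as a full non-event or deleted. Section 2.3 asks for neither.

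Transplant is the larger gap, because it ends the risk of drop-off altogether. If transplanted participants stay in the table, they count as non-events. If they are left out, which is one reading of the 47 in Section 3.0, participants are removed on a post-randomisation outcome. The same reading would also remove cirrhosis deaths, which Section 2.3 counts as drop-off events. With no rule written down, the choice could be made after the data are seen.

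At stake is whether the reported difference in drop-off reflects drop-off, or partly reflects who was transplanted or delisted for other reasons, and when.

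**Working it through.** **Inputs from the documents.** 47 per arm, 35% versus 14%, one-sided 0.10, stated power 80% (Section 9.3.2). Transplant risk 10% at 12 months, with a competing-event rate common to both arms (Section 9.3.1).

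**Assumptions.** The 12-month risk of other-reason delisting is not in the documents. It is set at 10% unless stated otherwise. All transplant or delisting differences between arms are assumed.

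**Step 1: the plan's own figure.** Summing two binomials (n = 47; 0.35 and 0.14) over every table that the one-sided Fisher test rejects at 0.10 gives power 81.4%. The stated 80% reproduces. True size at 35% versus 35% is 6.8%, below the nominal 10%.

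**Step 2: add removals.** Read 35% and 14% as net 12-month risks with exponential times, so each hazard is λ = −ln(1 − risk):
- Drop-off: −ln(0.65) = 0.431 on control and −ln(0.86) = 0.151 on pravastatin, a hazard ratio of 0.35.
- Transplant at 10% and other delisting at 10%: −ln(0.90) = 0.105 each.

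The crude proportion dropping off is (λ_drop / Λ) × (1 − e^(−Λ)), where Λ is the sum of the hazards:
- Control: (0.431 / 0.642) × (1 − 0.65 × 0.90 × 0.90) = 0.672 × 0.4735 = 31.8%.
- Pravastatin: (0.151 / 0.362) × (1 − 0.86 × 0.90 × 0.90) = 0.417 × 0.303 = 12.7%.

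**Step 3: power with balanced arms** (20,000 simulated trials per scenario, one-sided 0.10). The pooled z test uses the same crude proportions as Fisher's test. The log-rank test is cause-specific, censored at transplant and at other delisting.

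| Transplant / other delisting, both arms | Fisher | Pooled z | Log-rank |
|---|---|---|---|
| 0% / 0% | 81.6% | 87.8% | 87.6% |
| 10% / 10% | 77.1% | 84.8% | 84.9% |

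The gaps between Fisher and log-rank are 6.0 and 7.8 points. The pooled z test closes both without using any times, and the first gap exists with nobody to censor. The loss is therefore Fisher's conservatism. The gap grows to about 9 points (72% versus 81%) if transplant reaches 30% in both arms.

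**Step 4: equal drop-off hazards, unequal removal** (nominal 10%).

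| Control versus pravastatin | Fisher | Log-rank |
|---|---|---|
| Transplant 10% vs 10% | 6.8% | 10.0% |
| Transplant 10% vs 25% | 10.8% | 9.8% |
| Transplant 10% vs 35% | 15.1% | 10.2% |
| Other delisting 5% vs 25% (transplant 10% in both) | 12.6% | 10.0% |

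The mechanism shows in the third row. With transplant at 35% on pravastatin (λ = 0.431), crude drop-off there is (0.431 / 0.967) × (1 − 0.65 × 0.65 × 0.90) = 0.4455 × 0.620 = 27.6%, against 31.8% on control, although the drop-off hazards are identical.

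**Step 5: the opposite imbalance with a true effect.** With transplant 30% on control and 10% on pravastatin, and net drop-off 35% versus 14%, power is Fisher 65%, pooled z 75% and log-rank 83%. Here the crude proportions themselves cost about 8 points beyond Fisher's conservatism (83 − 75).

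**Step 6: the denominator.** Section 4.4 admits people who are inactive on the list or ineligible for transplant, so the number at risk of drop-off may be below 47 per arm. Exact one-sided Fisher power on 35% versus 14% is 76% at 40 per arm, 71% at 35 and 63% at 30. The documents do not give the share listed.

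**The case against.** The strongest defence is that the share of patients who drop off is a legitimate crude risk. Section 1.3 presents the aim as keeping patients eligible long enough to be transplanted, and a transplanted patient has not dropped off. Section 9.3.1 assumes the same competing-event rate in both arms and the trial is double-blind, so a large transplant imbalance is not expected. Section 2.3 gives drop-off no time origin, unlike RFS and OS. It is one of seven secondary endpoints in a phase II trial described as nondefinitive.

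Much of this stands. It rules out three stronger readings that a reader might infer:
- *The plan counts transplanted participants as successes.* No section says so. Exclusion is an equally available reading of Section 3.0.
- *Ignoring censoring costs power, or the 80% is miscalculated.* In balanced arms the gap is Fisher's conservatism, and 80% is correct for the test named.
- *The test will produce a false effect.* Under the plan's common rate, Fisher rejects about 7% under the null. At transplant 10% versus 25% it is still close to nominal.

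The defence does not remove the contradiction. If a crude risk is the target, the censoring sentence has no place in the definition and the handling of transplant still has to be stated.

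**Conclusion.** The inconsistency is real and needs no simulation: Sections 2.3 and 9.3 describe a censored time-to-event endpoint, and Section 9.3.2 names a test that cannot censor. The missing transplant rule is a second, separate gap.

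The numerical consequence is conditional. With balanced arms it is about 6 to 8 points of power, due to the choice of an exact test. Bias arises only if transplant or other-reason delisting differs substantially by arm. It can run either way: about 15% false positives instead of 10%, or power of about 65% instead of 83%, in the scenarios shown. These figures rest on exponential times, 35% and 14% read as net risks, 10% other-reason delisting, and imbalances that the documents do not predict.

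The choice of target also matters. A Gray-type cumulative-incidence test rejects 17.7% at transplant 10% versus 30% with equal drop-off hazards, because it too treats a transplant as no drop-off. Only the cause-specific comparison holds its level there (10.2%).

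**What to change.** In Section 9.3.2, replace the primary analysis of waitlist drop-off as follows:
- Restrict it to participants listed at randomisation.
- Analyse time from randomisation to drop-off with a cause-specific log-rank test and Cox model.
- Censor at other-reason delisting, as Section 2.3 already requires, and at transplant.
- State that the target is the cause-specific hazard of drop-off.
- Report cumulative incidence curves with transplant as a competing event as a descriptive companion. Say that they answer a different question and will also reflect any transplant imbalance.
- Keep Fisher's test as a descriptive summary.

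Use one name for the endpoint in Sections 2.3, 9.3 and 9.3.2.

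The cost is small. Delisting dates are already needed for the stated censoring rule, so the change is SAP wording plus a restated power basis. That restatement should use the expected number listed, which may be below 47 per arm.

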Liver stiffness and Liver fat fraction. The two-sample t-test will be used to compare the change in liver stiffness/fat fraction from 3 to 12 months between pravastatin and placebo groups. If the distribution of the change in liver stiffness/fat fraction is highly skewed so that the sample mean based on 47 measurements is not approximately normally distributed, the Mann-Whitney test will be used instead. Measurements of liver stiffness vary between 1.5 and 75 kPa. Therefore, we conservatively estimate the standard deviation of liver stiffness at 3 months as (75-1.5)/4 = 18.4. If X and Y denote the random variables of liver stiffness at 3 and 12 months, respectively, the Var(Y-X) = Var(X)+Var(Y)-2p Var(X) Var(Y), where p is the correlation coefficient between X and Y. Assuming a non-negative correlation between the measurements at 3 and 12 months and the same variance at 12 months  $\sigma$ 2, then a conservative estimate for the standard deviation of the change in liver stiffness is 1.4  $\sigma$ . Therefore, data from 47 patients per group achieve 80% power to detect an effect size of 0.5 using a two-sided two-sample t-test with 0.1 level of significance. We therefore have enough patients to detect clinically meaningful differences in mean liver stiffness. Here, the effect size is the ratio of the difference in the mean change between the two groups relative to the baseline standard deviation  $\sigma$ assumed to be the same for the treatment and control groups. Linear regression analysis will be carried out to estimate the adjusted pravastatin effect if there is evidence of imbalance between the two groups with respect to one or more baseline clinical and demographic covariates.

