**Change in biomarkers.** Two-sample t-test will be carried out to compare the change in biomarkers from baseline to each of the two follow-up time points, 6 and 12 months, between treatment and placebo groups. The Man-Whitney test will be used in the presence of highly skewed distributions and Fisher exact test will be used for dichotomous stratifications (high versus low). Assuming a common standard deviation of the change in biomarker from baseline to each time point between the two groups SD(diff), data from 47 patients per group achieve 80% power to detect an effect size of 0.72 using a two-sided two-sample t-test with a Bonferroni corrected 0.01 level of significance since we plan to test 10 biomarkers (0.1 / 10). Here, the effect size is the ratio between the difference in change of biomarkers between the two groups over SD(diff). Linear or logistic regression analysis will be carried out if there is evidence of imbalance between the two groups with respect to one or more baseline clinical and demographic covariates at each time point as in Aim 3.

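### Liver stiffness and fat fraction are analysed from month 3, when neither is measured, and the 80% power stated for stiffness is about 53% on the plan's own SD of change

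*Combined protocol and SAP*

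**What the plan says.** The liver stiffness and fat fraction paragraph of Section 9.3.2 plans a two-sample t-test to "compare the change in liver stiffness/fat fraction from 3 to 12 months between pravastatin and placebo groups". It then derives an SD for stiffness, again with month 3 as the starting point. It takes a quarter of the measurement range, (75 − 1.5)/4 = 18.4 kPa, as the SD at month 3 (σ). It assumes equal variance at month 12 and a correlation that is not negative, and concludes that "a conservative estimate for the standard deviation of the change in liver stiffness is 1.4" σ. From this it states that "data from 47 patients per group achieve 80% power to detect an effect size of 0.5 using a two-sided two-sample t-test" at the 0.1 level. It defines its terms by saying that "the effect size is the ratio of the difference in the mean change between the two groups relative to the baseline standard deviation" σ.

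Other sections describe a different interval. Section 2.3, Secondary Efficacy Endpoints, items 4 and 5, defines both endpoints as within-person change "between Study Visit 1 (0 month) and Visit 6 (12 month"). The opening of Section 9.3 says: "Differences in secondary endpoints from baseline to 12-month follow-up will be compared in the pravastatin and placebo groups".

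The next paragraph of Section 9.3.2, on biomarkers, uses another denominator: "the effect size is the ratio between the difference in change of biomarkers between the two groups over SD(diff").

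**The concern.** There are two faults in one paragraph.

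First, the analysis names a starting point at which no measurement is scheduled. Month 3 appears four times (the contrast, the SD, the definition of X and Y, and the correlation assumption), so it is not a single slip of the pen. The paragraph also contradicts itself, because it later calls σ the baseline SD.

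Second, the power figure appears to ignore the SD derived for it. The test is on change scores, so power depends on the difference divided by the SD of the change. If that SD is 1.4σ and the difference is 0.5σ, the standardised effect is well below 0.5.

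The plan concludes from this figure that it has enough patients to detect clinically meaningful stiffness differences. If the figure is wrong, a null stiffness result could be read as coming from an adequately powered comparison when it does not.

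**Working it through.** **Part 1: the interval.** Where each measurement is scheduled:

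| Place | Stiffness | Fat fraction |
|---|---|---|
| Section 2.3, items 4 and 5 | month 0 and month 12 | month 0 and month 12 |
| Section 6.2.2 (Visit 1) | listed | listed |
| Section 6.2.4 (Visit 3, month 3) | not listed | not listed |
| Section 6.2.7 (Visit 6) | listed | listed |
| Schedule of events (Section 6.4) | months 0 and 12 only | months 0 and 12 only |
| Section 9.3.2 analysis text | months 3 and 12 | months 3 and 12 |

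The study schema agrees with the schedule. A month-3 value is not planned anywhere, so a change from month 3 cannot be calculated.

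**Part 2: power for stiffness.** Inputs, all from Section 9.3.2: n = 47 per group, two-sided alpha 0.1, two-sample t-test, difference 0.5σ, SD of change 1.4σ, σ = 18.4 kPa. With df = 2 × 47 − 2 = 92, the critical value is 1.662. For a standardised effect d, the noncentrality is d × √(47/2) = 4.848d, and power comes from the noncentral t distribution.

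*Reproducing the stated 80%.*
- On the plan's definitions, d = 0.5/1.4 = 0.357 and the noncentrality is 1.731. Power is **53.0%** (52.3% with √2 in place of 1.4; 53.4% by the normal approximation). The stated figure is not reproduced.
- With 0.5 read in SDs of the change, d = 0.5 and the noncentrality is 2.424. Power is 77.7% (78.2% by the normal approximation), which is close to 80%. This reading leaves out the 1.4 factor.
- With 1.4σ and a one-sided 0.1 level, power is 67.1%, so a one-sided test does not explain the figure either.

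*What 47 per group can detect.* Power of 80% needs d = 0.517 SD of the change. In baseline units this is 0.517 × 1.4 = **0.72σ**, or 0.7234 × 18.4 = 13.3 kPa before rounding. The plan's 0.5σ is 0.5 × 18.4 = 9.2 kPa.

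*Patients needed.* Power of 80% at 0.5σ with SD of change 1.4σ takes 98 analysed per group.

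*Dependence on the correlation ρ.* The plan gives no value for ρ; the values below are assumptions. The SD of the change is σ√(2(1 − ρ)).

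| Assumed ρ | SD of change | Power at 0.5σ |
|---|---|---|
| 0 | 1.41σ | 52% |
| 0.25 | 1.22σ | 63% |
| 0.5 | 1.00σ | 78% |
| 0.75 | 0.71σ | 96% |

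Power of 80% needs an SD of change of at most 0.5/0.517 = 0.97σ, so ρ must be at least about 0.53.

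*Cross-check on the biomarker paragraph.* With alpha 0.01 and the effect in SDs of the change, d = 0.72 gives 80.3%, which matches that paragraph's claim. The mismatch is specific to the stiffness text.

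The plan gives no SD for fat fraction, so its power cannot be checked.

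**The case against.** The strongest reply is that 53% is the floor. Both stiffness readings come from the same patient on the same modality, so a correlation of zero is a bounding case, which the plan itself labels conservative. At a correlation of about 0.53 the stated 80% at 0.5σ is correct even with the effect size in baseline units, and that lies within the plan's assumption of a non-negative correlation. This stands as a limit on the size of the problem: true power may well exceed 53%. It does not rescue the statement, because the plan adopts 1.4σ and draws its power claim directly from it.

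A second reply is that the error may be only the denominator. Replacing the baseline SD by the SD of the change, and 0.5 by 0.52, would make the sentence correct. That is fair, and it is one form of the fix.

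On the interval, the intent is clear from Section 2.3 and the schedule, and no analyst could run the wrong contrast without month-3 data. The opening of Section 9.3 supports this for stiffness; its list does not name fat fraction, so for that endpoint the support is Section 2.3 and the schedule. The correction is one of wording, but the analysis text is still wrong as written.

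Finally, 18.4 kPa is a range-based guess applied to two modalities, so the kPa values are rough. This does not touch the 53%, which depends on the ratio 0.5/1.4, the group size and alpha.

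**Conclusion.** Both parts hold. The month 3 to month 12 contrast cannot be computed from the scheduled data and conflicts with the endpoint definitions. For stiffness, power at 0.5 baseline SD is 53% at the plan's own SD of change, not 80%, and the effect detectable with 80% power is about 0.72 baseline SD rather than 0.5.

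The power result assumes 47 analysed per group, equal variances, a t-test on change scores and an SD of change of 1.4σ. Over assumed correlations from 0 to 0.75, power runs from 52% to 96%. No power conclusion is drawn for fat fraction.

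The point should be fixed, but its reach is limited. These are secondary endpoints, and Section 9.3.1 justifies the sample size on time to recurrence, which does not change.

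**What to change.** Change every reference to month 3 in the stiffness and fat fraction paragraph of Section 9.3.2 to baseline (Visit 1), so that the contrast runs from Visit 1 to Visit 6. Then correct the stiffness power statement in one of two ways.

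- **(a) Keep the change-score t-test.** State the effect detectable with 80% power as about 0.72 baseline SD (about 13.3 kPa if σ is 18.4). Equivalently, define the effect size over the SD of the change, as the biomarker paragraph does, and state about 0.52. This costs a wording change and one restated number.
- **(b) Change the model** to an ANCOVA of the month-12 value on arm, baseline value and modality. The residual SD is σ√(1 − ρ²), with 90 df. The effect detectable with 80% power is then about 0.52 baseline SD (9.5 kPa) at ρ = 0, 0.50 at ρ = 0.25 and 0.45 at ρ = 0.5. These correlations are assumed, and modality is taken to explain no further variance. This also costs a change of analysis model in the text.

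Option (a) is enough to remove the error; (b) is an alternative. The 0.72 figure belongs to the t-test and should not be paired with the ANCOVA. Neither option needs new data or more patients.

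### The t-tests on change for the biomarkers, liver stiffness and fat fraction are valid but give up precision that pre-specified adjustment for the Visit 1 value would recover

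*Combined protocol and SAP*

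**What the plan says.** Section 9.3.2 of the combined protocol and SAP sets out the tests.

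- **Biomarkers:** "Two-sample t-test will be carried out to compare the change in biomarkers from baseline to each of the two follow-up time points", namely 6 and 12 months. Mann-Whitney is used if distributions are highly skewed, and Fisher's exact test for high/low splits. On power: "data from 47 patients per group achieve 80% power to detect an effect size of 0.72", two-sided at 0.01 (0.1 divided by 10 markers). The effect size is in units of the SD of the change.
- **Stiffness and fat fraction:** "The two-sample t-test will be used to compare the change in liver stiffness/fat fraction", with the change running from month 3 to month 12. On variability: "a conservative estimate for the standard deviation of the change in liver stiffness is 1.4" times the baseline SD σ. The claim is 80% power for an effect of 0.5 at a two-sided level of 0.1, with the effect defined relative to the baseline SD.
- **Regression:** for stiffness and fat fraction, "Linear regression analysis will be carried out to estimate the adjusted pravastatin effect if there is evidence of imbalance between the two groups" in baseline clinical and demographic covariates. For biomarkers, "Linear or logistic regression analysis will be carried out if there is evidence of imbalance between the two groups", with the same kind of covariates. Neither paragraph names the baseline value of the endpoint itself.

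Elsewhere, sections 6.2.2 and 6.4 schedule research blood, stiffness and fat fraction at Visit 1. Section 2.3 defines stiffness and fat-fraction change from Visit 1 (month 0) to Visit 6 (month 12). Section 6.4 has no month 3 measurement of either.

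**The concern.** Whoever has a change score also has the baseline value that went into it. Subtracting that value fixes its coefficient at 1, whatever the correlation. ANCOVA estimates the coefficient instead, and for any correlation below 1 the treatment comparison is tighter.

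The conditional regression does not supply this. Its trigger is an observed imbalance with no threshold, so the analysis is not fixed in advance, and the covariate that matters most is not on its list.

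At stake is precision on 12 continuous secondary endpoints, ten of them tested at 0.01, in an analysis set that section 9.2 expects to shrink from 130 to 94. A chance baseline difference d also shifts the expected change-score difference by −(1−ρ)d. One standard error of d is σ√(2/47) = 0.21σ. At ρ = 0.5 the shift is therefore about 0.10σ, a fifth of the 0.5σ target for stiffness.

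**Working it through.** **Inputs.** From section 9.3.2: 47 per arm; for biomarkers 0.72 SD of change, two-sided 0.01; for stiffness 0.5σ, two-sided 0.1, SD of change 1.4σ. The equal-variance assumption is the plan's own for stiffness and is extended here to the biomarkers. Only a non-negative ρ is stated, for stiffness between months 3 and 12, so values of ρ are assumed.

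**Step 1: reproduce the biomarker figure.** Non-centrality = 0.72 × √(47/2) = 0.72 × 4.848 = 3.49. With 92 df the critical value is 2.63 and power is 80.3%. The stated 80% is confirmed.

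**Step 2: variances.** Change score: 2σ²(1−ρ). ANCOVA: σ²(1−ρ²). The ratio is (1+ρ)/2, and the SD ratio is q = √((1+ρ)/2).

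**Step 3: biomarkers under ANCOVA.** Non-centrality becomes 3.49/q with 91 df. The detectable effect is the change-score value (0.718 before rounding) times q.

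| ρ | q | Non-centrality | Power at 0.72 | Effect detectable with 80% power, SD of change | n per arm for 80% |
|---|---|---|---|---|---|
| t-test on change | 1 | 3.49 | 80.3% | 0.72 | 47 |
| 0.3 | 0.806 | 4.33 | 95.3% | 0.58 | 32 |
| 0.5 | 0.866 | 4.03 | 91.6% | 0.62 | 36 |
| 0.7 | 0.922 | 3.79 | 87.3% | 0.66 | 41 |
| 0.9 | 0.975 | 3.58 | 82.6% | 0.70 | 45 |

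A simulation of 20,000 trials per ρ gave ANCOVA power of 95.2%, 91.5%, 86.7% and 82.4%.

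**Step 4: the plan's stiffness figure.** If 0.5 is read in units of the SD of change, power is 77.7%, close to the stated 80%. But the plan defines 0.5 relative to the baseline SD and takes the SD of change as 1.4σ. The standardised effect is then 0.5/1.4 = 0.357, the non-centrality 0.357 × 4.848 = 1.73, and power 53% (52% with √2 in place of the rounded 1.4). For 80% power the plan would need an effect of about 0.72σ, or about 98 patients per arm.

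**Step 5: stiffness under both analyses, effect 0.5σ, two-sided 0.1.**

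| ρ | SD of change | ANCOVA SD | Power, change | Power, ANCOVA |
|---|---|---|---|---|
| 0 | 1.414σ | 1.000σ | 52% | 78% |
| 0.3 | 1.183σ | 0.954σ | 65% | 81% |
| 0.5 | 1.000σ | 0.866σ | 78% | 87% |
| 0.7 | 0.775σ | 0.714σ | 93% | 96% |

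Neither ANCOVA table includes terms for the randomisation factors or imaging modality.

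**The case against.** The strongest reply is that this is a choice of efficiency, not an error. Under randomisation the t-test on change is unbiased over repeated trials, and its standard error already reflects chance baseline differences. These are secondary endpoints of a phase II screening trial, and the time-to-recurrence analysis is untouched. All of that stands. A reader might infer that the planned tests are invalid or biased; the documents do not support that.

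A reader might also infer that every stated detectable effect is larger than it needs to be. That is true for the biomarkers but not for stiffness. At ρ = 0 the detectable effect is 0.73σ by change score and 0.517σ by ANCOVA, both above the stated 0.5σ. The stiffness figure is too optimistic, for the reason in step 4.

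It is also tempting to say that baseline values exist for everyone. Section 3.1.2 has research blood taken from each participant, but it allows FibroScan when MRE is contraindicated, and the Study Schema pairs fat fraction with MRE. A baseline fat fraction is not assured for FibroScan patients, so neither is 47 per arm for that endpoint.

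The gain depends on an unknown ρ. The value ρ = 0 is the plan's worst case, not an expectation, and at ρ = 0.9 the biomarker gain is only about 2 points. This limits the promised benefit, but under equal variances the variance is never larger with ANCOVA.

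Finally, the Study Summary promises regression adjustment for chance differences, and section 9.3 says secondary endpoints follow a similar approach to the primary one, which section 9.3.1 adjusts for covariates. Neither names the endpoint's baseline value, and section 9.3.2, which is specific, makes the unadjusted test the main analysis.

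**Conclusion.** The point holds as avoidable loss of precision in secondary analyses. ANCOVA cuts the variance by (1−ρ)/2: 35%, 25%, 15% and 5% at ρ = 0.3, 0.5, 0.7 and 0.9. Over that range biomarker power rises by between 2 and 15 points. For stiffness the gain is 26 points at ρ = 0, 9 at ρ = 0.5 and 3 at ρ = 0.7. These figures assume equal variances at both times, 47 analysed per arm and the assumed values of ρ. The algebra is certain; the size of the benefit is not.

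Two related points need correction whichever test is kept. The month 3 start in section 9.3.2 conflicts with section 2.3 and the schedule, and the 80% power for stiffness does not follow from the plan's own definitions.

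**What to change.** 1. Make the main analysis of each biomarker, at 6 and at 12 months, an ANCOVA of the follow-up value on treatment, the Visit 1 value of the same marker and the randomisation factors in section 9.1 (site and initial HCC treatment type). Keep the t-test on change, or Mann-Whitney if highly skewed, as a sensitivity analysis. Modelling skewed markers on the log scale is an option, not a requirement.
2. For stiffness and fat fraction, first reconcile section 9.3.2 with sections 2.3 and 6.4. Then use the same model with the Visit 1 value, adding modality (MRE or FibroScan) for stiffness. State how patients without a baseline fat fraction are handled.
3. Restate the detectable effects on the ANCOVA variance with an explicit ρ or range, and correct the stiffness power.

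The cost is SAP wording and some degrees of freedom: one for the baseline term, four for five sites, one for modality where used, and a few for treatment type, whose levels section 9.1 does not list. No new data, visits or patients are needed.
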